**Clinical investigation of a new nanohybrid resin composite Venus Pearl in class 2
cavities– a multi-center study**

NCT01925040

Study Protocol and Statistical Analysis Plan

Date 15.08.2013

Objective of the study

The objective of this study is to compare the performance of the composite resin Venus Pearl (a development based on the material "Venus Diamond", Heraeus Kulzer, Hanau-Germany) and the commercially available control material Filtek Supreme XTE (3M/ESPE, Seefeld-Germany- available for the study center in Germany) and its equivalent material Filtek Supreme Ultra (3M/ESPE, Seefeld-Germany- available for the study center in the United States) for the restoration of class II-cavities. Primary endpoints of the study are: loss of the restoration, fracture of the restoration, postoperative sensitivity, marginal discoloration and marginal gap or step formation. Secondary endpoints are the evaluation of secondary caries, plaque accumulation and gingival reactions.

Ethics

The study is in accordance with the declaration of Helsinki. The study protocol will be assessed and approved by the ethical committee of Hannover Medical School as well as by the Institutional Review Board of the Oregon Health and Science University (OHSU). Each patient will receive a detailed information leaflet and has to declare in writing her or his consent to participate in the study. This written informed consent can be cancelled by the patient at any time without justification.

Study design

The study will be executed as a multi-center, single-blinded and randomized clinical investigation.

Multicenter, single-blinded, and randomized clinical investigation. Study sites are the Department of conservative Dentistry, periodontology and Preventive Dentistry at the Hannover Medical School, Hannover, Germany, and the Department of Restorative Dentistry at the Oregon Health and Science University, Portland, Oregon, USA. Coordination of the study at both study sites is done by the Hannover Medical School.

General information

Time frame of the study: 2 years (with optional extension to 4 years)

Number of patients/ restorations: 90 comparable cavities per Institution (180 total), randomization

Test material: n=90 (n = 45 per site)

Control material: n=90 (n = 45 per site)

Recruitment of patients

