Patients will be recruited by the Department of Conservative Dentistry, Periodontology and Preventive Dentistry of the Hannover Medical School and the Department of Restorative Dentistry of the Oregon Health and Science University (OHSU). Patients who require a class II restoration will be included in the study (see inclusion criteria). Each patient will be eligible to receive up to four restorations, with either a test or a control material. Patients will be given detailed information regarding the study before they are included in the study. Patients will receive an information leaflet and a copy of their signed informed consent form. Patients, who could not follow their examination appointments, will be contacted by phone to arrange a new appointment. Patients who miss three appointments will be classified as "drop-outs", which means that no further appointments will be scheduled for these patients regarding this study.

Inclusion criteria

- Patients should be 18 years and older.
- Study teeth should have an interproximal (Class II) carious lesion or an existing defective class II restoration requiring restorative therapy on premolars or molars.
- The maximum cavity depth determined by the radiograph will be D2 (Tyas classification).
- The teeth included in the study need to have a proximal contact with the adjacent tooth and be in occlusion with the opposing dentition.
- The teeth included in the study should be vital with no signs of pulpal pathology.
- Patients that report brushing regularly without severe gingival inflammation and/or extensive caries.
- Patients should have no allergies or systemic diseases which inhibit the treatment.
- Patients should have voluntary participation and sign a written informed consent form.
- Patients should be willing to participate in the recall/re-examination appointments.

Exclusion criteria

- Simultaneous participation in another study about dental restorative materials.
- Written informed consent form not signed.
- Nonvital pulp / periapical lesion.
- Insufficient oral hygiene despite detailed instructions.
- Pregnancy/ breast feeding before placement of the study restoration.
- Minors.
- Severe malocclusion/ malalignment/ traumatic occlusion/ bruxism.
- Known allergy to any components present in any of the materials that are used for this study.
- Unclear mucosal alterations, e.g. oral lichenoid reactions/lesions.

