- Severe medical complications (organ transplants, cancer, immune-compromised, long-term antibiotic or steroid therapy).
- Infectious diseases such as HIV/Aids, Hepatitis, etc.
- Application of bleaching products less than 14 days before placement of the restoration.
- Orthodontic treatment during the study.
- Xerostomia.
- Untreated periodontal diseases.
- Rampant or extensive caries present.
- Systemic diseases with potential oral manifestation.
- Sufficient isolation according to the criteria of adhesive techniques not possible, e.g. application of rubber dam.
- Direct adhesive restoration not indicated.
- Replacement of more than one cusp indicated.
- Dental fears patients.
- Cracked tooth syndrome in study tooth.

Assessment of restorations

Restorations will be assessed by the evaluator per site at baseline (1 week after placement), as well as after 6, 12 and 24 months. Evaluations will be documented within the source data (patient's documentation) and in the Case Report Form (CRF).

Photographs of the teeth will be taken after the cavity preparation and after the restoration has been placed and finished as well as at each evaluation appointment.

If the study will be extended to 4 years, two additional assessments will be done, after 3 and 4 years (36 and 48 months) and patients will be informed of a possible request for recall at years 3 and 4 at the initiation of the study.

The evaluations will be based on the Recommendations for Conducting Controlled Clinical Studies of Dental Restorative Materials, Science Committee Project 2/98 - FDI World Dental Federation (J Adhes Dent 9 (1), 121-147 (2007)).

Partial impressions of the study teeth will be taken at baseline and during all subsequent examinations of the restorations with an addition-type silicone material (Flexitime Putty and Correct Flow, Heraeus, Hanau-Germany) and a plastic inlay tray. These impressions will be used to determine the in-vivo wear of the restorations by means of replica using a resin material (DuroCit, Struers, Willich-Germany) by means of scanning electron microscopic-warden images.

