Secondary endpoints are the evaluation of secondary caries, plaque accumulation and gingival reactions and the comparison of the primary score at week 1, month 6, month 12 and month 24 after restoration. Beside this, the single components of the three categories of the primary endpoints will be compared.

Randomization, stratification and blinding

This is an observer-blind clinical trial, e.g. evaluators will not know the given treatment. Restorations will be distributed evenly between the control and the experimental groups using randomization lists.

The application of the two restorative materials is limited to premolars and molars and to achieve a uniform distribution of both tooth types, stratification with the strata premolar and molar will be performed in the randomization process. In addition randomization will be stratified by center.

Randomization will be performed centrally by the Institute of Biometrics to ensure admission before allocation. The randomization will not be based on patients' names, rather than on a scheduled visit, to avoid problems with patients that do not show up for the treatment.

In order to guarantee an objective evaluation at the different time points, the Case Report Form has separate sections for each evaluation, so that the evaluators only use the form for the present examination. Through this method, the evaluator cannot see which assessment he/she gave during previous examinations. These sections will only have the patient number information.

The treatment allocation and the corresponding patient ID will be kept in a separate file that is inaccessible for operators and evaluators.

Description of the primary analysis and key secondary analysis

In the primary analysis the superiority of Venus Pearl will be investigated. Therefore the primary analysis will be conducted on the ITT population, e.g. in all randomized patients. The missing values will be replaced as described below. For the comparison of the scores of the Venus Pearl and Filtek Supreme group an ANOVA will be performed 24 months after restoration. Here, center, tooth type and treatment will be incorporated as covariables. The study is successful if the 95 % confidence interval for the treatment effect (Venus Pearl – Filtek Supreme) is below 0.

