In the secondary analysis, caries (yes/no), plaque accumulation (yes/no) and BOP/ Pocket depths, will be examined with logistic regression models including center and tooth type as independent variables. Sensitivity analysis will be applied using mixed models.

If the study is extended to 4 years, the additional appointments taking place 3 and 4 years after restoration placement (late follow-up) will be evaluated descriptively using the same line as described above for the primary analysis.

Missing values

Missing values may be recorded when patients miss examination appointments. In this case the missing values will be replaced by the "last observation carried forward", where the assessment of the previous examination will be carried over to replace the missing value.

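### The logistic regression for secondary caries names no method for sparse events, and gives no finite treatment odds ratio if exactly one arm has no case

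*Combined protocol and SAP*

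**What the plan says.** The combined protocol and SAP lists caries among the secondary endpoints: "Secondary endpoints are the evaluation of secondary caries, plaque accumulation and gingival reactions". Its section *Description of the primary analysis and key secondary analysis* fixes the method: "caries (yes/no), plaque accumulation (yes/no) and BOP/ Pocket depths, will be examined with logistic regression models including center and tooth type". Treatment is not named as a term in that sentence, but a comparison of materials needs it, and it is taken as included here. The only supplement is a sensitivity analysis with mixed models.

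*General information* gives the size as "90 comparable cavities per Institution (180 total), randomization", with 45 restorations per arm at each site. *Recruitment of patients* allows up to four restorations per patient.

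The eligibility criteria bear on how often caries might occur. They exclude "Rampant or extensive caries present" and "Insufficient oral hygiene despite detailed instructions", and they admit "Patients that report brushing regularly without severe gingival inflammation and/or extensive caries". They also require that each study tooth has a carious lesion or a defective restoration. The plan gives no expected caries rate, no minimum number of events, no choice between Wald and likelihood-ratio inference, and no exact or penalised alternative.

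**The concern.** Secondary caries within 24 months may be uncommon, and 90 restorations per arm is a small denominator for an uncommon binary outcome. When one arm has cases and the other has none, treatment separates the data: the likelihood keeps rising as the treatment coefficient moves away from zero, so no finite maximum-likelihood estimate exists. Software then reports a very large coefficient with an enormous standard error, and the Wald p-value is close to 1 however marked the imbalance.

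At stake is the reporting of a named secondary endpoint. If default output were taken at face value, a clear imbalance would be reported as non-significant or not estimable. If the analyst switched to another method after seeing an empty arm, the choice would be post hoc.

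**Working it through.** **Inputs.** From *General information*: 45 per arm per site × 2 sites = 90 per arm, and 90 × 2 = 180 in total, which agrees with the stated total. The caries rate is not stated, so 0.5% to 5% is assumed, equal in both arms. Restorations are first taken as independent.

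**1. Probability of an empty arm.** For rate p and n per arm, P0 = (1 − p)^n. Exactly one arm is empty with probability 2·P0·(1 − P0), and both are empty with probability P0². For example, at p = 0.02 and n = 90, P0 = 0.98^90 = 0.162, and 2 × 0.162 × 0.838 = 0.272.

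| Assumed rate | P0 | Exactly one arm empty | Both arms empty |
|---|---|---|---|
| 0.5% | 0.637 | 46% | 41% |
| 1% | 0.405 | 48% | 16% |
| 2% | 0.162 | 27% | 3% |
| 3% | 0.064 | 12% | 0.4% |
| 5% | 0.010 | 2% | below 0.1% |

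Only the third column measures the problem. With 0 against 0 there is no treatment difference for any method to find.

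**2. Loss to follow-up and clustering (both assumed).** The same formula with 72 evaluable per arm (20% loss) gives 42%, 50%, 36%, 20% and 5% at the five rates. For clustering, patients were simulated with four restorations each in one arm and an intraclass correlation of 0.3. That gave P0 = 0.552, 0.304, 0.169 and 0.050 at 1%, 2%, 3% and 5%, so 2·P0·(1 − P0) = 49%, 42%, 28% and 9%. Both raise the figures clearly at about 2% and above. At 1% they change little, and at 0.5% the loss lowers the figure, because more trials then have two empty arms.

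**3. What the model returns for 6/90 against 0/90** (treatment, centre and tooth type as terms, cases spread over the strata):

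- Ordinary maximum likelihood, Wald: log odds ratio about 22 to 24 and standard error in the tens of thousands, depending only on where iteration stops; p = 0.999.
- The same model, likelihood-ratio test: p = 0.0035, with a lower 95% profile-likelihood limit of about 2.8 for the odds ratio and no upper limit.
- Firth penalised logistic regression: odds ratio 13.6, penalised likelihood-ratio p = 0.013.
- Fisher's exact test: p = 0.029.

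With 3/90 against 0/90 the ordinary estimate again diverges, while Firth gives a finite odds ratio of 0.14 for the empty arm against the other. Fisher's p is 0.25. All these p-values treat restorations as independent.

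**4. Mixed model.** A random patient intercept leaves the treatment coefficient unpenalised. With no case in one arm, the likelihood still rises without limit in that coefficient, so separation remains.

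**5. Empty centre or tooth type.** Suppose all cases fall in one centre, 4/45 against 2/45. The coefficient for centre diverges, but the treatment odds ratio comes from the centre with cases: (4 × 43)/(2 × 41) = 2.1, with log odds ratio 0.74 and standard error √(1/4 + 1/41 + 1/2 + 1/43) = 0.89. The treatment effect is still estimated.

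**The case against.** The strongest reply is that the plan never specifies Wald inference. A reader might infer that the planned model would hide a real caries problem. The documents do not support that: the likelihood-ratio test from the same model detects 6 against 0, with a smaller p-value than Firth or Fisher. This stands. What remains is that the plan does not choose that test either, and the odds ratio still has no finite estimate.

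A reader might also infer that separation is likely because the patients are at low caries risk. The criteria exclude extensive caries and poor hygiene, but they contain no caries-risk criterion, and every study tooth enters with a carious lesion or a defective restoration. With no rate given, the probability runs from nearly one half to 2%.

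A third tempting reading adds every trial in which some centre or tooth type has no case. Step 5 shows why those do not belong. Nor do the trials with two empty arms: counting them would give 87% at a rate of 0.5% and 65% at 1%, of which 41 and 16 points are 0 against 0.

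Finally, 6 against 0 is an illustration, not a typical outcome. At equal rates of 3% or less, an empty arm facing six or more cases occurs in under 0.7% of trials. With five against none, Fisher's p is already 0.059. So little significance is lost when the arms are truly equal; the usual loss is a finite estimate with an interval.

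**Conclusion.** The point holds as a gap in one secondary analysis. If exactly one arm has no caries case, the stated model yields no finite treatment odds ratio and its usual Wald output is uninformative, and neither the main text nor the mixed-model sensitivity analysis supplies a remedy. With 90 per arm, equal rates and independent restorations, this happens in 12% or more of trials at each tabulated rate from 0.5% to 3%, and in about 2% at a rate of 5%. The rates are assumptions, as are the loss and clustering figures. The planned model can still detect a difference through a likelihood-ratio test, so the plan cannot be said to conceal one. The primary ANOVA and the success criterion are untouched. The change is worth making because it is cheap. Confidence is moderate, because the size depends on a rate that the documents do not give.

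**What to change.** In *Description of the primary analysis and key secondary analysis*, state that secondary caries is analysed by Firth penalised logistic regression with treatment, centre and tooth type as terms, using penalised profile-likelihood confidence intervals and tests. Report the number of cases per arm with a risk difference and its interval.

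Firth regression and standard intervals for a risk difference treat restorations as independent, while a patient may contribute up to four. Add a check that allows for this, such as a patient-level bootstrap or a permutation test that respects patients and the way restorations were allocated. When an arm is empty, every bootstrap resample of it is empty too, so the permutation test is the more informative of the two in that case.

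The cost is a few sentences in the SAP and standard software, plus modest programming for the clustering check. The statistical downside is slight shrinkage of the odds ratio toward 1. Plaque and bleeding can stay with ordinary logistic regression if they prove common.

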Side effects that are associated with the treatment such as local inflammation due to an inadequately placed or polished restoration, and/or oral lichenoid reactions that are in direct vicinity to the study restoration, will be documented in detail and the patient affected will be excluded from the study. In this case, the restoration will be replaced by another material as soon as possible. In addition, a restoration that fractures due to a mechanical failure of the material will also be replaced as soon as possible. It is possible to have an irreversible pulpitis develop after placement of the restoration, as often times happens during routine dental treatment. In this case, the subject will be excluded from the study and will have to continue with the appropriate treatment at the dental office of their choice at their own expense.

Biostatistical analysis

Study design

The goal of this clinical trial is to show that Venus Pearl (a development based on the material "Venus Diamond", Heraeus Kulzer, Hanau – Germany) has a better score than the commercially available control material (Filtek Supreme XTE, 3M/ESPE, Seefeld – Germany and Filtek Supreme Ultra, 3M/ESPE, USA) for the restoration of class II-cavities. Patients older than 18 who show an interproximal (Class II) carious lesion or an existing defective restoration requiring therapy on premolars or molars will be included.

For the determination of the superior outcomes of both fillings a pre-specified evaluation scheme will be used.

The assessment of the replacement will be performed at four time points (1 week, 6 months, 12 months and 24 months after replacement). For the primary analysis the score will be considered 24 months after the replacement.

The primary endpoint will be a mean score calculated as following: There are three aspects to be assessed: aesthetic, functional attribute and biological parameters. For each aspect there are respectively four categories where each has to be assessed on a scale from 1 to 5. Thereby 1 means clinically excellent, 2 means clinically good and 3 means clinically disappointing. This assessment form is given in FDI World Dental Federation (J Adhes dent 9 (1), 121 – 147 (2007)). For each

patient the points of the 12 different evaluation criteria (four categories in the three parts) will be summed up resulting in a score that ranges from 12 to 60.

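### Pocket depth goes to logistic regression with no binary coding, so the gingival comparison rests on an unstated, information-losing cut-off; analyse depth as a continuous outcome, separate from BOP, and name treatment in the models

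*Combined protocol and SAP*

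**What the plan says.** The Combined protocol and SAP names the endpoint in *Objective of the study* and again under *Biostatistical analysis, Study design*: "Secondary endpoints are the evaluation of secondary caries, plaque accumulation and gingival reactions". Neither place defines a gingival reaction or gives a unit or threshold.

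The analysis is in *Description of the primary analysis and key secondary analysis*. The outcomes are listed as "In the secondary analysis, caries (yes/no), plaque accumulation (yes/no) and BOP/ Pocket depths", and the sentence goes on to the model: "plaque accumulation (yes/no) and BOP/ Pocket depths, will be examined with logistic regression models including center and tooth type as independent variables". No visit is named for these models.

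For the primary score, the paragraph just before says: "Here, center, tooth type and treatment will be incorporated as covariables". The secondary sentence is followed by "Sensitivity analysis will be applied using mixed models", with no outcome, link function or fixed effects.

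The only other scale that might cover a periodontal finding is the one behind the primary score: "For each aspect there are respectively four categories where each has to be assessed on a scale from 1 to 5". One of its three aspects is biological, but the text does not connect it to BOP or pocket depth.

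**The concern.** A binary logistic model needs a two-valued outcome. Two of the listed outcomes have one and pocket depth does not. To fit the model, someone must choose a depth above which a site counts as an event, and the plan leaves that choice open. Two analysts following the text could report different gingival comparisons from the same data, and either would use less of the information than the depths contain.

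Two smaller gaps sit in the same sentence. The slash between BOP and pocket depth does not say whether they are two outcomes or one. The listed terms also leave out treatment, which is the effect the trial exists to estimate. Gingival reaction is one of three clinical secondary endpoints, so the sentence should be exact enough to program from.

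**Working it through.** **No figure to reproduce.** The document gives no SD, event rate, effect size or power for this endpoint. The core of the point is textual; the arithmetic only shows its size.

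**Step 1: look for a coding.**

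| Item | Coding in the document |
|---|---|
| Caries | yes/no |
| Plaque accumulation | yes/no |
| BOP | none |
| Pocket depth | none; no unit, cut-off or probing site |

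*Assessment of restorations* describes visits, photographs, impressions and the cited FDI recommendations, but not probing. No section supplies the missing rule.

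**Step 2: information kept by a cut-off.** For a normal variable and a small shift, a cut-off exceeded by a proportion p keeps the fraction φ(z)² / [p(1−p)], where z is the cut-off in SD units and φ the standard normal density. The planned number of restorations is 180, from "Test material: n=90 (n = 45 per site") and the same for control.

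- p = 0.5: z = 0, φ = 0.3989; 0.1592 / 0.25 = 0.637; 180 × 0.637 ≈ 115
- p = 0.2: z = 0.842, φ = 0.2800; 0.0784 / 0.16 = 0.490; 180 × 0.490 ≈ 88
- p = 0.1: z = 1.282, φ = 0.1755; 0.0308 / 0.09 = 0.342; 180 × 0.342 ≈ 62

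The equivalents 115, 88 and 62 are nominal, because they treat all 180 restorations as independent and observed.

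**Step 3: how far the open rule moves the comparison.** All values here are assumed: depth normal with SD 1.0 mm, means 2.5 and 2.9 mm, recorded in whole mm; BOP 30% in both arms and independent of depth; 90 independent restorations per arm; two-sided 5% level. In whole mm, at least 3 mm means a true depth above 2.5 mm. The event rates are then 1 − Φ(0) = 50.0% and 1 − Φ(−0.4) = 65.5%. The other rows follow in the same way.

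| Cut-off | Event rates | Power, depth alone | Power, BOP or deep | Power, BOP and deep |
|---|---|---|---|---|
| ≥3 mm | 50.0% v 65.5% | 56% | 36% | 13% |
| ≥4 mm | 15.9% v 27.4% | 47% | 19% | 15% |
| ≥5 mm | 2.3% v 5.5% | 20% | 5% | 9% |

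With depth kept continuous, 0.4 / 1.0 × √(90/2) = 2.683; 2.683 − 1.96 = 0.723; power Φ(0.723) ≈ 77%. Allowing for whole-mm rounding, the variance is 1 + 1/12 and the SD 1.041; 2.683 / 1.041 = 2.578; 2.578 − 1.96 = 0.618; power about 73%. Either is above every entry in the table.

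As a cross-check on Step 2, a median split should give √0.637 × 2.683 = 2.141; 2.141 − 1.96 = 0.181; power about 57%, close to the 56% in the first row.

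**Step 4: model terms side by side.** Primary model: center, tooth type, treatment. Secondary models: center, tooth type.

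**The case against.** **Treatment.** A reader might infer that the secondary models do not compare the materials at all. The document does not support that. The word *including* need not introduce a complete list, the stated objective is to compare the two materials, and the primary model names treatment. The natural reading is a treatment comparison adjusted for center and tooth type. What stands is that the word is missing.

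**The slash.** A reader might infer a composite of BOP and depth. Nothing states one. The sentence speaks of models in the plural, and a slash can simply list two measures, in which case no combination rule is needed. The two right-hand columns of the table apply only if a composite was meant.

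**Choice after seeing the data.** A reader might infer that the cut-off would be picked once the depths are known, with an inflated error rate. The document does not say when or by whom it would be set. If an analyst tried ≥3, ≥4 and ≥5 mm and kept the best, the chance of at least one p<0.05 with no true difference would be about 13% (assumed mean 2.8 mm, SD 1, 90 independent restorations per arm). It runs from 9% to 13% for means of 2.2 to 3.2 mm and SDs of 0.8 to 1.2, and is about 9% with only the two lower cut-offs. That describes a behaviour the plan does not forbid, not one it announces.

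**Loss of information.** Dichotomising does not always discard most of it: a median split loses 36%.

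**The unseen form.** Evaluations rest on cited FDI recommendations, and the CRF is not reproduced. Depth may be recorded as a grade, or even as yes/no. This is a fair limit: the document implies, but does not confirm, that depths exist as numbers. It does not rescue the sentence, because the text makes no link from that form to these models.

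**Importance.** Study success depends only on the confidence interval for the primary score. That is correct, and it bounds the severity.

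**Conclusion.** The point holds in a limited form. Logistic regression is assigned to pocket depth without the binary coding it requires, and no other section supplies one. The model can be run only after an unstated cut-off is chosen. That cut-off keeps roughly 64% to 34% of the information over exceedance rates of 50% to 10%, assuming an approximately normal depth and a small difference. Under the assumed values in the working, power with depth alone is 20% to 56% against about 73% to 77% with depth kept continuous. Those powers illustrate the effect and are not predictions. With up to four restorations per patient and some drop-out, actual precision may be lower under any of these analyses.

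Whether BOP and depth are separate outcomes is unclear and should be stated. The missing treatment term is a drafting omission. None of this touches the primary analysis or its success criterion. It should be corrected because the gingival endpoint cannot be programmed unambiguously from the text as it stands.

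**What to change.** Rewrite the secondary-analysis sentence so that it does the following:

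1. Analyse pocket depth at the study restoration as a continuous outcome in a linear model with treatment, center and tooth type. Allow for several restorations in one patient (*Recruitment of patients* permits up to four), for example by a patient random effect or cluster-robust standard errors.
2. Analyse BOP separately as yes/no by logistic regression with the same terms.
3. Name treatment as the effect of interest in the caries, plaque and BOP models.
4. State the visit to which these models apply.

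First check how the CRF records depth. If it holds only a grade, use an ordinal model or a cut-off fixed and documented before unblinding. If a binary depth outcome is preferred for clinical reading, a pre-specified cut-off would also close the gap, with the loss of information shown above.

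If depths are recorded as numbers, the cost is a change of wording in the analysis plan and one more secondary estimate, since BOP and depth are reported separately. Sample size and the primary analysis stay as they are.

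### The models for caries, plaque and BOP/pocket depth, and the primary ANOVA, have no patient term although a patient may have up to four restorations; mixed models are only an unspecified sensitivity analysis

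*Combined protocol and SAP*

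**What the plan says.** All references are to the combined protocol and SAP.

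- **Several restorations per patient.** *Recruitment of patients*: "Each patient will be eligible to receive up to four restorations, with either a test or a control material".
- **Unit counted.** *General information*: "Number of patients/ restorations: 90 comparable cavities per Institution (180 total), randomization", with 90 per material and 45 per material at each site. The number of patients is not given.
- **Unit allocated.** *Randomization, stratification and blinding*: "Restorations will be distributed evenly between the control and the experimental groups using randomization lists". Strata are tooth type (premolar or molar) and center. The same section says that randomization does not go by name, in a sentence that ends "rather than on a scheduled visit, to avoid problems with patients that do not show up for the treatment".
- **Secondary models.** *Description of the primary analysis and key secondary analysis* marks caries and plaque as yes/no and continues: "BOP/ Pocket depths, will be examined with logistic regression models including center and tooth type as independent variables". The next sentence is the only mention of mixed models: "Sensitivity analysis will be applied using mixed models".
- **Primary model.** The same section plans an ANOVA of the 24-month score: "Here, center, tooth type and treatment will be incorporated as covariables".

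No random patient effect, GEE, robust variance or limit of one restoration per patient appears anywhere.

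**The concern.** Plaque, gingival bleeding and caries depend on the patient's hygiene and caries risk, so restorations in one mouth tend to agree. A model that treats them as independent misstates the standard error of the treatment effect. It comes out too small if a patient's restorations share one material, and too large if the two materials are balanced within the patient. It is about right with one restoration per patient, or on average if each restoration is randomized independently.

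The sensitivity analysis does not repair the main intervals, and no outcome, random effect or link is given for it. The same omission affects the ANOVA, which carries the trial's only success rule.

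Two smaller points sit in the same sentence of the plan. BOP and pocket depth are named together without a coding, and it is not clear whether they are one outcome or two. If the coding is not fixed, it could be chosen after the data are seen. Treatment is not listed among the model terms.

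**Working it through.** **Stated figures.** 45 per arm per site × 2 sites × 2 arms = 180, which agrees with the plan. The sample size cannot be re-derived, because no effect size, event rate, power or within-patient correlation is given. At one, two or four restorations per patient, 180 restorations come from 180, 90 or 45 patients.

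**Assumptions.** Within-patient correlation (ICC) 0.1 to 0.3; restorations per patient m = 1.5, 2 or 4. Here 1.5 is the restoration-weighted mean for 90 patients with one and 45 with two: (90×1 + 90×2)/180. The documents give only the maximum of four. A two-sided 5% test is also assumed for the secondary endpoints, for which the plan states no level.

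**Same material within a patient.** Design effect DE = 1 + (m − 1) × ICC; true error = 2 × (1 − Φ(1.96/√DE)); effective restorations per arm = 90/DE; correct interval width relative to the planned one = √DE.

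| m | ICC | DE | True error | Effective n per arm | Width factor |
|---|---|---|---|---|---|
| 1.5 | 0.1 | 1.05 | 5.6% | 86 | 1.02 |
| 1.5 | 0.3 | 1.15 | 6.8% | 78 | 1.07 |
| 2 | 0.1 | 1.10 | 6.2% | 82 | 1.05 |
| 2 | 0.3 | 1.30 | 8.6% | 69 | 1.14 |
| 4 | 0.1 | 1.30 | 8.6% | 69 | 1.14 |
| 4 | 0.3 | 1.90 | 15.5% | 47 | 1.38 |

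**Materials split evenly within every patient.** The variance factor is 1 − ICC, that is 0.9 to 0.7. True error is 3.9% to 1.9%, a loss of power.

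**Simulation of plain logistic regression at a 30% event rate** (180 restorations, beta-binomial outcome, 20,000 runs per setting, no covariates or missing data; each pair is ICC 0.1 / 0.3):

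| Layout | Same material | Split within patient |
|---|---|---|
| m = 1.5 | 5.2% / 6.8% | 4.5% / 3.4% |
| m = 2 | 6.0% / 8.3% | 3.9% / 2.0% |
| m = 4 | 8.8% / 15.2% | 3.9% / 1.9% |

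With each restoration allocated independently, the error was 4.3% to 4.9%. A second simulation included center and tooth type (4,000 runs per setting, m = 2 and 4, ICC 0.1 to 0.5) and gave 4.9% to 5.4%.

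**Rare outcomes.** At an assumed 5% event rate with shared material, plain logistic regression with center and tooth type (3,000 runs per setting) had an error, among runs that could be fitted, of 3.2% to 4.5% at m = 2 and 4.2% to 8.3% at m = 4. A separate run gave about 2% to 7%. The formula figures therefore do not describe caries if caries is rare.

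**Patient-clustered alternative.** GEE with independence working correlation and robust standard errors gave 4.5% to 5.7% over all 18 settings at 30% events, and 4.2% to 5.1% with a t reference on patients minus 2 degrees of freedom. At 10% events with 45 patients it reached 6.6% (5.8% with t). At 5% events the logistic fit failed in 5% to 17% of runs, and GEE error in the rest was 2.5% to 6.0%. A mixed model was not simulated.

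**Primary ANOVA.** The same design-effect algebra applies approximately to a difference in mean scores, with the ICC of the score, which is also not given.

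**The case against.** The strongest reply is that the plan allocates by restoration. Cavities are counted, restorations are distributed, and tooth type is a property of the tooth that cannot stratify a patient who has both kinds. The scheduled-visit phrase explains itself as a guard against no-shows, so it may concern timing only. Under independent allocation the error is about 5%. This stands as the better supported reading, but it is not stated as a rule. The recruitment sentence can be read either way, and nothing says what happens when one visit covers several teeth.

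A second reply is that the planned mixed models cover clustering. They may, but the text does not say so, and with four assessment times they could equally be meant for repeated visits.

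A third is that analysis is per patient, since the score and the ITT population are worded that way. No rule combines several restorations into one value, however, and a patient with a premolar and a molar has no single tooth type to enter as a covariate.

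Two further points stand in full. The inflation figures belong to common outcomes. The plan also attaches no decision rule to the secondary endpoints, so for them the harm is misstated intervals and p-values, not a false declaration of success.

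A reader might infer that the trial's error rate is inflated, even to 15%. The documents do not support that: it needs shared material and four restorations in every patient. A reader might also infer that treatment is left out of the logistic models. The purpose of the analysis makes it plainly intended, so this is a drafting gap.

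**Conclusion.** The concern holds as an omission whose direction is unknown. Neither the main logistic models nor the ANOVA accounts for the patient, and the one analysis that might is unspecified. For a common outcome (30%) and ICC 0.1 to 0.3, a nominal 5% test has a true error of about 5% under independent restoration-level allocation. It is about 6% to 9% if two restorations share a material, about 15% at the extreme of four each, and about 4% to 2% if materials are split evenly. The effect is small if most patients have one restoration. ICC, cluster size and event rate are all assumptions.

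It would be too strong to say that a clustered model is valid in every case. It stayed near 5% for a common outcome, but ran somewhat high with 45 patients at 10% events and could not always be fitted at 5%. It is still the better main analysis, because it depends far less on the unstated allocation rule. The change should be made; confidence is medium.

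**What to change.** Amend the analysis section before unblinding.

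1. For caries, plaque and BOP (each yes/no), name one patient-clustered model as the main analysis. It can be logistic GEE clustered on patient, with independence working correlation, robust standard errors and a t reference on patients minus 2 degrees of freedom. Or it can be the already planned mixed model, in logistic form with a named random patient effect. Include treatment as the effect of interest, center and tooth type. If both are reported, state that the mixed-model odds ratio is patient-specific and on a different scale from the GEE one.
2. In the primary ANOVA, add a random patient effect or patient-clustered robust standard errors.
3. Set in advance a minimum number of caries events, pooled over arms and counted blind, below which only counts by arm are reported.
4. Analyse pocket depth separately from BOP, with its scale fixed before unblinding. If it is a measurement, a linear mixed model with the same terms and a random patient effect would serve.

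Stating how several teeth in one patient are allocated would also help the reader.

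The cost is SAP wording and slightly more analysis work. If a patient's restorations share one material, intervals widen by about 2% to 14% (m = 1.5 to 2), and by up to 38% with four each. If materials are split evenly within every patient they narrow by about 5% to 16% (√0.9 = 0.95, √0.7 = 0.84).
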